During the index ED visit, patients will be offered video-based patient education employing storytelling aimed at promoting evidence-based gout management. These stories will be shown on a tablet computer used in the ED and also available to patients on the web. This health literacy-appropriate and culturally-sensitive educational “storytelling” intervention will aim to improve patient- knowledge of gout, readiness to adopt available treatments, understanding of potential therapeutic complications of therapies and lifestyle approaches to preventing future flares (e.g. weight loss, increased exercise, improved nutrition, and decreased alcohol use).^{55, 56} The educational materials will include stories about the appropriate need to start and continue on urate lowering therapy (ULT), which is generally recommended by groups such as the ACR when gout flares occur more than 2 times per year; for flares occurring in the setting of gout comorbidities such as significant chronic kidney disease (grade 2 or greater) or urolithiasis; or if there is evidence of gouty tophi on examination or by imaging studies.⁸⁰ Stories will emphasize the key importance of seeking appropriate follow-up care for gout management; the primary outcome of this study. This intervention component will be provided on a tablet computer delivered by ED research assistants to the patient and/or their family, if present. Content of the videos will be adapted to include information on the link between flares and uncontrolled hyperuricemia and used to promote shared decision-making,^{53, 81} self-efficacy for gout management,^{55, 56} and to improve adherence to ULT, and reduce reliance on opioid analgesics.^{42, 43}

The ED team will provide care referral to relevant medical services that might benefit their gout under their existing health plan, such as primary care services (if they do not already have a primary care physician) or to the Cahaba Medical Group (UAB Site) for those under insured or without insurance.

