A lay patient navigator working with and trained by the UAB MHRC and the gout research team will contact patients seen in the UAB ED via phone within 72 hours following the ED visit. During this initial phone conversation the navigators will: 1) conduct a baseline assessment to identify barriers to attending an outpatient visit for gout care (e.g. transportation) and to adhering to gout treatment recommendations (medications, diet, exercise) and, 2) determine the level of support and assistance (e.g. transportation support) needed by patient. The patient navigator will help facilitate the follow-up visit with a primary care/gout specialist, identify any barriers (e.g. lack of trust in primary care physician or/and healthcare system),⁸² and provide institutional/community resources that can be mobilized for the patient. The navigator will conduct two additional follow-up calls at approximately one month and at one week (anticipated) prior to the visit to confirm the appointment time, the level of support needed (as needs may have changed), and encourage him/her to keep their appointment. In the unlikely event that the appointment with the PCP/gout specialist is sooner than one month, this one-month pre-appointment call will be eliminated and the navigator will have only two calls with the patient (**Figure 2**). Navigators will be trained using didactic materials, including case simulations and role-play, that will be prepared as part of this study. Participants at all sites will be provided a card with a group picture of the patient navigator team that will contact them.

Figure 2. Study Workflow – Patient Navigation

B.5.3 Usual Care Arm -ED Encounter.

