Similar to the intervention arm patients randomized to the control arm at both institutions will be provided with a follow usual care referral to relevant medical services that might benefit their gout under their existing health plan, such as primary care services (if they do not already have a primary care physician) or to the Cahaba Medical Group at the UAB Site. Timing for this planned follow-up will be consistent with typical wait times to see a specialist or general practitioner for their gout. In most US metropolitan areas, given the limited national supply of rheumatologists, the average wait time is 9 to 10 weeks to see a new patient.⁸³ To address the issue of an “attention control,” all persons randomized to the control arm will receive existing educational e-material on the tablet computer on routine preventive health measures including vaccinations and age-appropriate preventive care measures unrelated to gout or the study outcomes. These materials will also be emailed to them.

B.5.4 Gout CORT Registry and Biorepository Sample Collection (Aim 3)

Blood specimens and synovial fluid (if drawn) will be collected for the Gout CORT Registry and Biorepository at the time of the enrollment visit in the ED. Blood specimens and synovial fluid (if collected as part of ED visit) will be collected by ED study coordinators/RAs in PAXGene RNA/DNA tubes and stored in -80° freezer until transport to the UAB Division of Clinical Immunology and Rheumatology for processing and long-term storage (see Shipping Manual). All samples will be labeled with a patient identification (PID) number and date of visit. Documentation of specimens will be stored in the lab computer database, secured and password protected, and distributed to only to authorized personnel. Banked specimens will be available for future research in gout, hyperuricemia, and gout-comorbid conditions (e.g. hypertension, diabetes) and will include samples for genomic DNA, RNA expression, and epigenetic analysis.

B.6 Informed Consent (IC)

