Patients and study coordinators will enter baseline demographic, gout history, patient reported outcomes (PROs) directly into electronic case report forms into a 21CFR and HIPAA compliant REDCap (Nashville, Tennessee) system. We will host REDCap on one of several access-controlled, encrypted servers housed at UAB. Subsequent PROs and other outcome data will be captured by phone in the same REDCap database by the study teams. Baseline laboratory data and medication data will be obtained from our respective EMRs and will be reviewed during the phone calls and by the research assistant during the ED visit.

B.8 Study Outcomes

Study outcomes (**Table 2**) will be collected from patients at 6 weeks and 3 months following the initial ED visit with questionnaires deployed using computer assisted telephone interviews (CATI) programmed in REDCap. Validated items about gout flares and gout medications have been used in the past by our team.⁸⁴

B.8.1 Primary outcomes Aim 1 and 2.

The primary outcome of aim 1 will be the ability of the alert to successfully identify gout patients. For aim 2, it will be the proportion of patients that have a follow-up visit addressing gout in the 3-month period after the ED visit. Many gout patients are not adherent with their follow-up visits due to a lack of awareness of the consequences of untreated

gout, poor care access, and/or inadequate assistance to obtain a follow up visit. Even rapidly-scheduled outpatient visits (next business day) following an ED encounter are only attended by 73% of those seen in a recent study and rates of post-ED follow-up for many chronic disease are closer to 50%.^{91, 92} Moreover, most patients, ~80%, leave the ED with knowledge deficits that impact adherence and outcomes.^{93, 94} Having a usual source of primary care and establishing continuity of care after an ED visit is critical to optimal disease outcomes in all chronic diseases including gout.³⁰⁻³² This data will be captured both by self-report on surveys (this will be the primary study outcome) and by review of EMR data within our respective healthcare systems. While self-report will be impacted by recall and possible social desirability bias, this should be non-differential (bias towards the null).⁹⁵ EMR data will be more accurate for some outcomes but will miss any gout care delivered outside our urban Southeastern medical centers and their satellite facilities.

B.8.1.1 Secondary outcomes - Aim 2

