Secondary Outcomes / Covariates				
Social Determinants of Health				
Environmental and social factors	X			
Gout medical care				
Number of gout flares (Gaffo criteria) ^{79, 84}	X	X	X	
Rates of urate lowering therapy (ULT)**	X	X	X	
ULT adherence		X	X	
Opioid prescriptions*	X	X	X	
Weight reduction		X	X	
Healthcare resource utilization (visit number)				
ED visits (indicative of recidivism)*		X	X	
Hospitalizations*		X	X	
Health-related quality of life				
European Quality of Life (EQ-5D) ⁸⁶⁻⁸⁸	X	X	X	
Shared decision making: CollaboRATE scale ⁹⁰		X	X	

* gout follow-up within 3-months of ED visit. ** Assessed through chart or system review

randomized 2:1 stratified by race/ethnicity, to the intervention (storytelling +/- patient navigation) or control arm (usual care). All intervention arm patients in the UAB ED also will be assigned lay navigators to provide personalized support for care transitions and access to post-gout flare medical services needed for preventing recurrent flares.

The following procedures will be completed during the index ED visit:

- Review inclusion/exclusion criteria for registry participation
- Informed Consent
- Review of current/past gout status and medication chart review
- Pain Assessment
- Laboratory
 - Serum uric acid (from chart review)
 - Sample banking
- Survey assessments
 - HRQL
 - SDOH

Laboratory draw will be done in conjunction with ED care blood draw when possible. At the conclusion of visit, participants randomized to navigator arm will be provided navigators picture, contact information, and informed that they will receive a call w/in 72 hours.

B.9.1.2 *Patient Navigator Contact*

72 hours post ED visit

During this initial phone conversation the navigators will: 1) conduct a baseline assessment to identify barriers to attending an outpatient visit for gout care (e.g. transportation) and to adhering to gout treatment recommendations (medications, diet, exercise) and, 2) determine the level of support and assistance (e.g. transportation support) needed by patient. The patient navigator will help facilitate the follow-up visit with a primary care/gout specialist, identify any barriers (e.g. lack of trust in primary care physician or/and healthcare system), and provide institutional/community resources that can be mobilized for the patient.

4 weeks post ED visit and 24-48 hours prior to appointment (anticipated)

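### The design does not secure the claim that self-report error in the Aim 2 primary outcome is equal between arms and toward the null, and the captured EMR visits have no assigned analysis to check it

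*Combined protocol and SAP*

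**What the plan says.** On the source of the primary outcome, B.8.1 states: "This data will be captured both by self-report on surveys (this will be the primary study outcome) and by review of EMR data". It then says of the error: "While self-report will be impacted by recall and possible social desirability bias, this should be non-differential (bias towards the null". It adds that the EMR will miss care given outside the participating systems.

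On what each arm receives:
- **Intervention (B.5.2):** "Stories will emphasize the key importance of seeking appropriate follow-up care for gout management; the primary outcome of this study". Navigators phone to confirm the appointment and to "encourage him/her to keep their appointment" (also B.9.1.2). B.9.1.1 describes the arms as "the intervention (storytelling +/- patient navigation) or control arm (usual care"; D.2 lists navigation at all four sites.
- **Control (B.5.3):** a referral, plus attention-control material on "age-appropriate preventive care measures unrelated to gout or the study outcomes".

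On timing, Table 2 collects the primary outcome at both week 6 and month 3, with the footnote "gout follow-up within 3-months of ED visit". B.8.1, B.10.2 and B.11 also use 3 months, and B.10.2 plans models at both times. But B.9.1.4 describes the 3-month survey as assessing secondary outcomes, and the visit-schedule footnote in B.9.1.5 puts primary assessment at up to 6 weeks. B.9.1.3 places the debrief after the first survey; B.9.1.6 places it after the primary outcome has been ascertained.

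On analysis, B.10.2 specifies logistic regression by intent to treat. B.10.3, which covers secondary outcomes, mentions multiple imputation as a sensitivity analysis. In Table 2 the note "Assessed through chart or system review" is attached only to urate-lowering therapy rates.

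**The concern.** Error that is equal in both arms shrinks a difference in proportions and leaves the false-positive rate at its nominal level. Unequal error can create a difference where none exists, in either direction. The B.8.1 sentence invites the reader to treat a positive result as conservative.

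Here the arms differ on exactly the behaviour that patients later report. One arm is told that the follow-up visit matters and may be phoned about it; the other hears nothing on gout beyond its referral. That could raise over-reporting or sharpen recall in the intervention arm. It need not do either. At stake is how the main result may be read, and whether data already being collected are used to check it.

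**Working it through.** **Inputs from B.11.** Two-sided alpha 0.05; 200 analysed, 2:1, so about 67 control and 133 intervention; control rate 30%; relative risk 1.68; 30% non-response at 3 months (280 to 196).

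**The plan's power.** The intervention rate is 0.30 × 1.68 = 0.504 and the pooled rate is (0.30 + 2 × 0.504)/3 = 0.436. The standard error is 0.0744 under the null and 0.0709 under the alternative. Power = Φ[(0.204 − 1.96 × 0.0744)/0.0709] = Φ(0.82) = 79%. Exact enumeration at 67/133 gives 79.6%. The stated 80% is reproduced.

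**Reporting model.** Reported rate = p × recall + (1 − p) × f, where p is the true attendance rate and f is the share of non-attenders who report a visit.
- Equal error in both arms: the reported difference is (p₂ − p₁)(recall − f), which is smaller than the true difference. Here B.8.1 would be right.
- Unequal error with no true effect: the reported difference is p(recall₂ − recall₁) + (1 − p)(f₂ − f₁), which is generally not zero and can take either sign.

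The documents give no error rates, so those below are **assumptions**. Example: p = 0.30 and f = 0.10 in the intervention arm only gives 0.30 + 0.70 × 0.10 = 0.37 against 0.30.

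Two-sided rejection with no true effect (exact enumeration, pooled z-test, 67 vs 133):

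| Assumed error | p = 30% | 40% | 50% |
|---|---|---|---|
| None | 5.0% | 5.2% | 4.8% |
| f = 5%, intervention only | 7.7% | 7.0% | 6.1% |
| f = 10%, intervention only | 16.3% | 12.5% | 10.3% |
| f = 10%, controls only | 17.4% | 13.4% | 9.8% |
| f = 10%, both arms | 5.1% | 4.9% | 5.0% |
| Recall 95% intervention, 85% control; f = 5% both | 6.9% | 8.6% | 9.8% |
| Recall reversed; f = 5% both | 7.4% | 8.8% | 10.3% |

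At p = 30%, 16.1 of the 16.3 points favour the intervention; in the controls-only row, 17.3 of the 17.4 favour control.

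If the plan's assumption is right, the cost is power: for 30% vs 50.4% it falls from 80% to 69% (f = 10% in both arms) or 66% (recall 90%, f = 5% in both arms).

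**What the EMR check can bear (assumed capture).** With all 280 randomised (93 vs 187) and equal capture of 80%, 70% or 60% of visits, EMR-only power for 30% vs 50.4% is 79%, 70% or 60%. If capture is 60% in one arm and 70% in the other, rejection with no true effect is 9% to 10%, favouring the arm with better capture. The confirmation rate rests on few claims. If 70% are in-system and f = 10% in the intervention arm, there are 133 × 0.37 × 0.7 ≈ 34 claims against 67 × 0.30 × 0.7 ≈ 14. The standard error of the difference is about 7 to 11 points; the lower end takes control confirmation as 100%, so that arm adds no variance.

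**Missing answers.** 280 × 0.30 = 84 patients would lack a 3-month answer. B.11 expects this to be slightly uneven by arm and labels the remaining 196 per protocol, while B.10.2 promises intent to treat. Neither section gives a rule for the 84.

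**The case against.** Every error rate above is assumed, and the reverse cases favour control about as strongly. The table shows that unequal error distorts the test, not that this trial has unequal error. The B.8.1 sentence is hedged and cites a source that is not available here. There are real safeguards: a referral in both arms, an attention control, participant blinding at enrollment, computer-assisted telephone interviews (B.8) and 6-week contact by the Coordinating Center rather than the navigators (B.9.1.3). All of this stands and limits the point. It does not establish equal error: the attention control balances contact but not the message, and interviewer masking is not stated.

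Table 2 and B.10.2 also show that the primary outcome is collected and modelled at both times. Two-wave collection of a 3-month outcome explains why primary-outcome questions appear in the 6-week survey, and the 6-week model uses answers given before the debrief. What remains in conflict is the B.9.1.4 description, the B.9.1.5 footnote and the place of the debrief.

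The EMR is an imperfect yardstick. B.5.2 and B.5.3 refer patients at the UAB site to the Cahaba Medical Group, and the documents do not say whether EMR review covers it.

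A reader might infer that the debrief itself biases the comparison. It reaches both arms, so it weakens blinding without proving an arm difference.

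**Conclusion.** The statement that error is non-differential and toward the null is asserted, not secured, and B.10 assigns no EMR analysis to the primary outcome. Under the assumed 10% excess over-reporting at 30% attendance, nominal 5% rejection becomes about 16% in favour of the intervention or 17% in favour of control; equal error leaves it at 5% and costs power. These figures illustrate sensitivity and do not estimate this trial's bias.

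A reader might go further and conclude that self-report inflates the intervention effect, or that the EMR should replace it. The documents support neither: direction and size are unknown, and the EMR misses outside care, possibly unequally by arm.

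The timing conflict is textual and needs no assumption. Its effect on the debrief is conditional: only if the primary time is 3 months does the debrief precede complete ascertainment, contrary to B.9.1.6. The trial remains analysable. This should be fixed, chiefly because it governs how a positive result may be described.

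**What to change.** 1. **B.8.1.** Delete the clause calling the error non-differential and toward the null. State that reporting error may differ by arm in an unknown direction.
2. **B.10.2.** Keep self-report primary. Record the date and clinic of each reported visit. Prespecify two supportive sensitivity analyses: an EMR-only analysis of all randomised patients, and a descriptive EMR confirmation rate by arm for in-system visits, with confidence intervals. State their limits: outside care is missed, coverage of the Cahaba clinic is unstated, capture may differ by arm, and claims are few. Say whether survey interviewers know the arm.
3. **Timing.** Reconcile B.8.1, Table 2, B.9.1.3 to B.9.1.6, B.10.2 and B.11. If the primary time is 3 months, move the debrief to after the 3-month survey. If it is 6 weeks, the debrief can stay and the 3-month definitions must change.
4. **Missing answers.** In the intent-to-treat analysis, count a gout visit reported at 6 weeks as a success when the 3-month survey is missed, since it falls within the window. State how the other non-responders are handled; simply dropping them would recover only successes. State that the imputation sensitivity analysis in B.10.3 covers the primary outcome, with the 6-week answer in the model and a range of delta shifts. No single delta should be presented as restoring the 5% error rate. For example, if 80% of attenders and 60% of non-attenders respond, the built-in log-odds shift is ln[(0.2/0.4)/(0.8/0.6)] = −0.98, so a delta of −1 merely returns the assumption. Making imputation the primary method is not required.

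The cost is SAP wording, two survey items, EMR review that is already planned and, if the primary time is 3 months, a later debrief.

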- 1) *Gout medical care*- Self-reported flare rates will be captured using the Gaffo gout flare criteria (developed and validated at UAB) and adapted to self-report.^{79, 84} Uptake of evidence-based gout care will include self-reported prescribing rates of ULT and opioid analgesics. We also will determine medication adherence based on participant self-report. Since obesity is a major factor associated with gout and weight reduction will be addressed in the stories (as well as how to avoid foods high in purines), we will examine changes in self-reported weight between study entry and follow-up.
- 2) *Healthcare resource utilization*- outcomes will include repeat ED visits (ED recidivism) and re-hospitalization rates. Outpatient visits to primary care and/or rheumatologists will be measured as the primary outcomes.
- 3) *Health-related Quality of Life (HRQL), Shared Decision Making and Perception* – HRQL will be recorded using the European Quality of Life (EQ-5D) scale⁸⁶⁻⁸⁸. We will use the CollaboRATE scale, a brief patient survey focused on shared decision making, to measure perception of shared decision making from a patient perspective.⁹⁰

B.8.1.2 Key Covariates Aim 2. To better describe the population we are studying and to adjust for any potential imbalances that might not be addressed by randomization, we will collect key social determinants of health as covariates at baseline and for dynamic measures, again at month 3. These will include: health literacy,¹⁰³ economic factors, transportation, discrimination and other key demographics such as educational level, community social economic status, and personal measure of socioeconomic status will be assessed using measures from the Behavioral Risk Factor Surveillance System.¹⁰⁸ We will also capture the time of “stories” watched as a measure of dose-response of the intervention.

B.9 Study procedures and Assessments

B.9.1.1 Screening, Enrollment, and Randomization (see Step-By-Step Guide in Appendix)

Following the gout alert activation in the ED, research assistants housed in the UAB ED will interview patients in person to further determine possible eligibility, and if potentially eligible, to consider randomization. Patients classified as having acute gout based on the Gaffo criteria who meet the inclusion/exclusion criteria will be

Table 2. Specific Aim 2 Outcomes and Covariates

	ED	WK 6	Mo 3	Time Point
Primary Outcome				
Outpatient primary care or specialist visits targeted for gout*		X	X	

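### The urate-lowering therapy (ULT) outcome is called uptake of evidence-based care, but it has no stated denominator, ignores ULT use recorded at the ED visit, and is not tied to the circumstances the protocol cites for ULT

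*Combined protocol and SAP*

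**What the plan says.** In B.8.1.1, under gout medical care, the plan states: "Uptake of evidence-based gout care will include self-reported prescribing rates of ULT and opioid analgesics". Table 2 lists the ULT rate at the ED visit, week 6 and month 3, with a footnote giving its source as "Assessed through chart or system review". ULT adherence is a separate row, at week 6 and month 3 only.

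B.5.2, describing the content of the stories, says ULT is "generally recommended by groups such as the ACR when gout flares occur more than 2 times per year". It adds "for flares occurring in the setting of gout comorbidities such as significant chronic kidney disease (grade 2 or greater) or urolithiasis", and tophi on examination or imaging.

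Entry under B.2.1 needs a current flare but none of these circumstances, and B.3 expects the alert to pick up patients first diagnosed at the index visit. B.1 names appropriate use of therapy among the things the study will test.

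B.10.3 analyses secondary outcomes by t-test or linear regression, names no denominator or baseline ULT term for this outcome, and calls these endpoints hypothesis-generating.

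**The concern.** Three things are left open.

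- **Baseline users.** A patient already taking ULT on arrival and still taking it at 3 months adds to the rate in either arm, although the intervention started nothing. The plan records ED-visit ULT but does not say it will be used.
- **The label.** The rate is presented as evidence-based uptake. A patient outside the B.5.2 circumstances who is not on ULT lowers it, and one who is on ULT raises it. If the rate goes up, the report cannot say whether use rose where the protocol's own text says ULT is generally recommended, or elsewhere.
- **The source.** B.8.1.1 says self-report and the Table 2 footnote says chart or system review. These can disagree, since B.8.1 accepts that the EMR misses care given outside the participating systems.

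At stake is how one secondary outcome is read, and the freedom to choose its denominator after the data are seen.

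**Working it through.** **1. The plan's own figure.** B.11 gives power only for the primary outcome: 200 patients, 2:1, control 30%, relative risk 1.68 (so 50.4%), two-sided 0.05. I used the pooled two-proportion formula:

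power = Φ[(|p_I − p_C| − 1.96·SE0) / SE1], where SE0 = √[p̄(1−p̄)(1/n_C + 1/n_I)] and SE1 = √[p_C(1−p_C)/n_C + p_I(1−p_I)/n_I].

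With n_C = 66.7 and n_I = 133.3 this gives 79.4%, which matches the stated 80%. No ULT rate, effect or power is stated, so everything below is illustrative.

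**2. Inputs.** From B.11: 280 × 0.70 = 196 responders, or 131 intervention and 65 control. The non-response figure is the one B.11 gives for the primary outcome. All ULT rates are assumed.

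**3. Patients already on ULT.** Let b be the share on ULT at the ED visit. Assume 90% continue in both arms, and new starts among non-users are 35% intervention and 15% control. The all-patient rate is 0.90b + (1−b) × new-start rate. At b = 0.30:

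- Control: 0.27 + 0.70 × 0.15 = 37.5%. Intervention: 0.27 + 0.70 × 0.35 = 51.5%.
- All patients: SE0 = 0.0757, SE1 = 0.0742, (0.14 − 0.1484)/0.0742 = −0.11, power 46%.
- Non-users only (91.7 and 45.5 patients): SE0 = 0.0817, SE1 = 0.0727, (0.20 − 0.1602)/0.0727 = 0.55, power 71%.

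| b | All-patient difference | Power | New-start difference | Power |
|---|---|---|---|---|
| 10% | 18 points | 72% | 20 points | 82% |
| 30% | 14 points | 46% | 20 points | 71% |
| 50% | 10 points | 27% | 20 points | 55% |

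This rests on equal continuation. At b = 0.30, if continuation were 70% control and 90% intervention, the all-patient rates would be 0.21 + 0.105 = 31.5% and 0.27 + 0.245 = 51.5%, with power 76%. That exceeds the 71% from new starts alone.

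**4. The cited circumstances.** Let f be the share of patients in the B.5.2 circumstances, with assumed ULT use of 30% control and 50% intervention, and 10% in both arms among the rest. At f = 0.60:

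- Control: 0.6 × 0.30 + 0.4 × 0.10 = 22%. Intervention: 0.6 × 0.50 + 0.4 × 0.10 = 34%. The difference is 12 points, power 40%.
- Only those in the circumstances (78.6 and 39 patients): 20 points, power 54%.
- The same comparison is 31% against 47% at f = 0.50, and 60% against 67% at f = 0.80.

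**5. The assumption that drives step 4.** At f = 0.60, let the intervention also raise ULT among the other patients:

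- From 10% to 20%: intervention rate 0.30 + 0.08 = 38%, difference 16 points, power 62%.
- From 10% to 30%: intervention rate 0.30 + 0.12 = 42%, difference 20 points, power 81%.

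Both exceed the 54% of the restricted analysis. If use among the others is zero in both arms, the risk ratio is unchanged and only the risk difference shrinks.

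**6. What the all-patient rate cannot show.** Step 4 gives 22% against 34%. The same result arises if use in the cited circumstances is 30% in both arms and use among the others goes from 10% to 40%: 0.6 × 0.30 + 0.4 × 0.40 = 34%. The planned figure is identical in the two cases.

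**The case against.** A reader might infer that the plan definitely counts every patient and that the arm difference is therefore diluted. The documents support neither. The all-patient denominator is the ordinary reading of an unqualified rate, but it is read from silence. Dilution requires little or no effect among patients outside the cited circumstances. Yet B.4 and the messages in Appendix G.1 promote gout medication without that restriction, and step 5 shows the restricted analysis can then have less power.

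Other objections also stand:

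- The share outside the circumstances is unknown and may be small. The comorbidity clause in B.5.2 is open-ended, and A.1 describes kidney disease as strongly associated with gout and endemic in the region.
- B.5.2 describes video content. It does not say that ULT outside the listed circumstances is wrong.
- Tophi, kidney grade and stones are not itemised in B.9.1.1, although it includes "Review of current/past gout status and medication chart review". Under B.7, baseline medication and laboratory data are also reviewed in phone calls, and the visit schedule places phone contacts after randomisation.
- Randomisation should balance baseline users on average, the adherence row partly covers continuation, and the endpoint is hypothesis-generating.

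These points limit the size of the problem. They do not supply the missing denominator, give recorded ED-visit ULT a role, or let the rate carry the evidence-based label.

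**Conclusion.** The point holds as a gap in definition and interpretation. As written, the outcome mixes new starts with continuation and mixes use inside the cited circumstances with use outside them. The direction of any distortion from the second mixture is not known: the arm difference may be diluted or inflated.

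Using ED-visit status gives the clearer gain. Under equal continuation of 90% and new starts of 35% against 15%, power goes from 46% to 71% with 30% baseline users, and the gain is smaller when fewer patients start on ULT. It is not guaranteed, because an effect on continuation can reverse it. The breakdown by cited circumstances is justified by interpretability, since step 6 shows two quite different results with the same headline rates. No claim that restriction always gains power should be made.

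The consequence is modest: one secondary outcome, with the primary outcome and sample size unaffected.

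**What to change.** In B.8.1.1, Table 2 and B.10.3:

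- State the denominator for the ULT rate at 6 weeks and 3 months.
- Analyse ULT by status at the ED visit: new starts among non-users and continuation among users, or one model adjusted for baseline use.
- Keep the all-patient rate. Add a pre-specified breakdown by whether baseline gout history and chart data meet the circumstances listed in B.5.2, using only information dated before randomisation and reporting missing items. This classifies patients by the protocol's own text and takes no view on which indication is clinically right.
- Reconcile self-report (B.8.1.1) with chart or system review (Table 2 footnote), and use the same source at baseline and follow-up. Otherwise a patient treated elsewhere could look like a new start.

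The cost is SAP wording, one derived baseline variable, and a check that the baseline form captures annual flare count, tophi, kidney disease grade and stones. The downsides are smaller denominators for one hypothesis-generating outcome and possibly incomplete tophus and kidney data, which would misclassify some patients in the breakdown.
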